5.3.4 Termination of Study

This study may be prematurely terminated if there is sufficient reasonable cause, including but not limited to:

- Unexpected, significant, or unacceptable risk to subjects
- Interim analyses by the DSMB.
- Insufficient compliance with protocol requirements
- Data are not sufficiently complete and/or not evaluable
- Regulatory authorities decide that study should be terminated

If the study is prematurely terminated for harm, current subjects will complete follow up, and no further subjects will be enrolled. If the study is terminated due to benefit, then the study will immediately convert into an open-label prospective cohort to collect further observational data on the safety and efficacy of the intervention, up to the IRB approved recruitment limit.

6 STUDY INTERVENTION/INVESTIGATIONAL PRODUCT

6.1 Study Product Description

6.1.1 Acquisition

FDA-approved formulation of hydroxychloroquine will be purchased.

6.1.2 Formulation, Packaging, and Labeling

The study medicines will be packaged by the MHealth Investigational Drug Services. Dispensed medications will be delivered by courier (e.g. Fedex) to study participants.

Labels will include: "Caution: New Drug – Limited by Federal Law to investigational use. Keep out of reach of children."

[figure not shown]
6.1.3 Drug Description:

Hydroxychloroquine sulfate

6.1.4 Formulation: 200mg tablet (= 155 mg base of chloroquine)

6.1.5 Pharmacokinetics:

- Absorption: Rapid and almost completely
- Distribution: Widely distributed into body tissues
- Metabolism: Partially hepatic to main metabolite of desethylchloroquine
- Excretion: Urine (>=50% as unchanged drug); acidification of urine increases elimination
- $C_{max} = 1.2 \text{ nmol/mL} = 1.2 \text{ } \mu\text{mol/L} = 1.2 \text{ } \mu\text{M}$ at 400mg single dose.[15]
- $T_{max} = 2.4 \text{ hours}$
- $T_{1/2} = 172 \pm 39 \text{ hours} = 7.1 +1.6 \text{ days}$
- $AUC_{last} = 75.4 \pm 47 \text{ nmol/h/mL}$
- This C_{max} is in the therapeutic window for SARS-COV2 activity.
- Steady state doses for 400mg dose is $974 \text{ } \mu\text{g/L} = 2.24 \text{ } \mu\text{M}$ [16], thus a 600mg dose should generate approximately $3.4 \text{ } \mu\text{M}$, which is above the EC_{50} of viral inhibition of $1.3 \text{ } \mu\text{M}$ ($EC_{50} = 50\%$ inhibition; however, the more inhibition the better, likely).

Population PK parameter modeling: 5 day regimen

[figure not shown]
[figure not shown]

Figure courtesy of [name] of College of Pharmacy, Univ. of Minnesota

The EC50 has been reported as 0.72 μM [5], although this is not a precise measurement, and should be view with a range of error present (but not reported). The EC50 is the point of 50% maximal inhibition, so more drug would be better (balanced against toxicity and drug supply). The percentage of persons achieving a 24 hour level above the EC50 is as follows (**Figure**).

6.1.6 Product Storage and Stability

Store at room up to 30° C (86° F). Dispense in a tight, light-resistant container.

6.2 Dosage, Preparation, and Administration of Investigational Product

Drug/Device Handling:

Hydroxychloroquine or placebo will be dispensed by the MHealth Investigational Drug Service (IDS) Pharmacy. To do so, study investigators will send a prescription to the IDS Pharmacy, the pharmacy will randomize the subject, and dispense the appropriate study medicine. The medicine will then be provided to research volunteers via FedEx / courier delivery in the United States.

6.3 Modification of Investigational Product for a Participant

With mild side effects, participants will be instructed to split the 3 tablet daily dosing into multiple times per day.

In the event of substantial side effects, participants may discontinue the study medication and stay in the study to complete follow up.

6.4 Accountability Procedures for the Investigational Product:

Accountability will be via self-report at the day 5 virtual visit.

6.5 Assessment of Subject Compliance

Adherence will be via self-report at day 5 virtual visit.

6.6 Concomitant Medications/Treatments

Participants may receive other concomitant medications or therapies, and will be asked to report these in regards to other therapies received on day 1, day 14, and in the event of hospitalization.

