FDA cautions against use of hydroxychloroquine or chloroquine for COVID-19 outside of the hospital setting or a clinical trial due to risk of heart rhythm problems

Close supervision is strongly recommended

“The FDA is aware of reports of serious heart rhythm problems in patients with COVID-19 treated with hydroxychloroquine or chloroquine, often in combination with azithromycin and other QT prolonging medicines. We are also aware of increased use of these medicines through outpatient prescriptions. Therefore, we would like to remind health care professionals and patients of the known risks associated with both hydroxychloroquine and chloroquine. We will continue to investigate risks associated with the use of hydroxychloroquine and chloroquine for COVID-19 and communicate publicly when we have more information.”

“Hydroxychloroquine and chloroquine can cause abnormal heart rhythms such as QT interval prolongation and a dangerously rapid heart rate called ventricular tachycardia. These risks may increase when these medicines are combined with other medicines known to prolong the QT interval, including the antibiotic azithromycin, which is also being used in some COVID-19 patients without FDA approval for this condition. Patients who also have other health issues such as heart and kidney disease are likely to be at increased risk of these heart problems when receiving these medicines.”

Mitigation of Risk: The inclusion / exclusion criteria exclude cardiac risk factors, chronic kidney disease, and anti-arrhythmia medicines. On 24 April, additional QT prolonging medicines are excluded.

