5.2 Subject Exclusion Criteria

- Current Hospitalization
- Contraindication or allergy to hydroxychloroquine
- Retinal eye disease
- Concurrent malignancy requiring chemotherapy
- Known glucose-6 phosphate dehydrogenase (G-6-PD) deficiency
- Known chronic kidney disease, stage 4 or 5 or receiving dialysis
- Known Porphyria
- Weight < 50 kg
- Structural or ischemic heart disease
- Personal or Family history of prolonged QT
- Current use of: hydroxychloroquine, chloroquine, or cardiac medicines of: flecainide, Tambocor; amiodarone, Cordarone, Pacerone; digoxin or Digox, Digitek, Lanoxin; procainamide or Procan, Procanbid, propafenone, Rythmal; or sotalol.
- Current use of QT prolonging medicines of:
 - Antimicrobials: levofloxacin, ciprofloxacin, moxifloxacin, azithromycin, clarithromycin, erythromycin, ketoconazole, itraconazole, or mefloquine
 - Antidepressants: amitriptyline, citalopram, desipramine, escitalopram, imipramine, doxepin, fluoxetine, wellbutrin, or venlafaxine
 - Antipsychotic or mood stabilizers: haloperidol, droperidol, lithium, quetiapine, thioridazine, ziprasidone
 - Methadone
 - Sumatriptan, zolmitriptan

Rationale for inclusion / exclusion criteria:

* As of 20 March 2020, testing is limited in many U.S. states and locales due to insufficient supplies. Thus, outpatient testing may not be available. A person with known exposure to a confirmed COVID-19 case with subsequent compatible symptoms is eligible for enrollment, if testing is not available. If a symptomatic person tests negative for SARS-CoV-2, they are not eligible for enrollment.

Mean Incubation period is ~5.2 days, thus we wish to limit enrollment to those with a higher risk of progression and deliver study medicine in a time period to intervene to prevent disease or ameliorate disease (i.e. start of study medicine by ≤ 4 days after exposure). The current (as of March 17, 2020) delays in testing makes this window particularly tight, and it may need to be relaxed in the future via protocol amendment.

In clinical practice of tropical medicine, chloroquine or hydroxychloroquine are prescribed without any baseline laboratory testing or monitoring.

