7 STUDY SCHEDULE

Screening Online Questionnaire

- Email [contact] or go to www.covidpep.umn.edu if you have been exposed to or diagnosed with COVID19
- You will be sent an email with information about our clinical trial
- A URL link will be provided for you to take the online screening survey

Medication Shipped

- Study medicine will be shipped overnight to your address
- Study medicine should arrive by 10:30am (Mon-Sat)
 - If you enroll after ~12pm on Sat or Sun, will arrive Tue.
- Take 4 tablets of the study medicine with some food or milk

Online Survey (Day 1)

- You will receive an email with a link to an online survey from [contact]. If not received, check your spam folder.
- Take the second dose of 3 tablets 6-8 hours after the first.
- Take other medicines \geq 4 hours apart from the study medicine

Study Days 2-4

- You should take 3 tablets each morning
- If you develop upset stomach, you may separate the pills; for example 1 at breakfast, 1 at lunch, and 1 at dinner.
- We will send a brief Day 3 survey

Online Survey (Day 5)

- You will receive an email with a link to an online survey
- This should be the same day you finish the study medicine
- A brief follow up survey will also be sent on Day 10 to ask if you have any COVID19 symptoms

End of Study Survey (Day 14)

- You will receive an email with a link to an online survey
- Unless you have developed symptoms, this marks the end of the study. We will ask if you wish to participate in future studies.
- If you were hospitalized or have pending tests, we will reach out to you every 2 weeks.

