7.5 Early Termination Visit

If participants develop new / worsening symptoms of coronavirus, they will be directed to their healthcare provider and/or local public health authority for clinical care. We will follow up of hospitalized patients for resolution of their SAE for up to 90 days to assess their final outcome. Participants will be sent the Hospitalization eCRF 14 days after hospitalization is reported with repeats in 14 day intervals until the participant is discharged from the hospital.

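### The QT-prolonging and antiarrhythmic drug restrictions apply only at entry; section 6.6 then allows any medication, and the protocol body does not say what to do if a listed drug is prescribed during or soon after dosing

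*Combined protocol and SAP*

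**What the plan says.** - **Entry restriction.** Protocol section 5.2 lists cardiac medicines and then a longer group under the words "Current use of QT prolonging medicines of". The second group includes azithromycin, clarithromycin, erythromycin and three fluoroquinolones. Both items are worded as current use. Sections 5 and 7.1 apply eligibility by self-report on a web form.
- **Reason for it.** The rationale after 5.2 attributes the medication exclusions to possible drug interactions. Section 2.3.1 reproduces an FDA caution: "These risks may increase when these medicines are combined with other medicines known to prolong the QT interval, including the antibiotic azithromycin".
- **Stated mitigation.** Section 2.3.1 answers the caution with eligibility alone: "The inclusion / exclusion criteria exclude cardiac risk factors, chronic kidney disease, and anti-arrhythmia medicines", and then "On 24 April, additional QT prolonging medicines are excluded".
- **After entry.** Section 6.6 reads "Participants may receive other concomitant medications or therapies", and adds that participants "will be asked to report these in regards to other therapies received on day 1, day 14, and in the event of hospitalization". It has no prohibited list and does not refer back to 5.2.
- **Other instructions on co-medication.** The participant schedule in section 7 asks for other medicines to be taken at least "4 hours apart from the study medicine". Section 2.3.1 gives a similar spacing rule for antacids.
- **Where ill participants go.** Section 7.5 says of those with new or worsening symptoms that "they will be directed to their healthcare provider and/or local public health authority for clinical care".

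**The concern.** An interaction risk runs for as long as the two drugs are in the body together. A restriction that is checked once at screening does not cover a drug started on day 2. The participants most likely to be offered such a drug are those who are ill at entry (one of the two planned cohorts of 1500) or who fall ill during follow-up. They are treated by outside providers who may not know about the trial. The caution reproduced in 2.3.1 itself notes that azithromycin was being used in some COVID-19 patients.

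At stake is a foreseeable safety step. Followed as written, 6.6 lets a participant start azithromycin and carry on with the study tablets, with only a spacing rule for guidance.

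**Working it through.** There is no figure in the plan to reproduce. The main check is a comparison of texts; two small calculations show when an instruction could still change exposure.

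**Step 1. Is there a post-entry rule anywhere in the protocol body?**

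| Section | What it offers | Does it cover a listed drug started after entry? |
|---|---|---|
| 5.2 | Exclusion for current use | No, entry only |
| 2.3.1 | Mitigation through eligibility; antacid spacing | No |
| 6.3 | Dose splitting; stopping for substantial side effects | No |
| 6.6 | Other therapies allowed; asked about on day 1, day 14 and at hospitalization | Recording only |
| 7 | 4-hour spacing | Timing only |
| 7.6 | On-call physician by email | Only if the participant sees a reason to write |
| 4.5 | Optional EKG, once daily for 7 days | Optional detection, not avoidance |
| 5.3.2, 5.3.3, 11.4 | Withdrawal at any time; those who stop tablets stay in follow-up | Permits stopping but does not prompt it |
| 14.3 | Comprehension check on randomization to hydroxychloroquine or placebo | No listed item on interactions |

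No section joins the 5.2 list to the period after entry.

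**Step 2. How much study drug could an instruction avoid?** Inputs from section 4.1: 800 mg, then 600 mg on day 1, then 600 mg daily for 4 days. Total = 800 + 600 + 4 × 600 = 3800 mg.

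| Stop after day | Taken (mg) | Avoided (mg) | Avoided / 3800 |
|---|---|---|---|
| 1 | 1400 | 2400 | 63% |
| 2 | 2000 | 1800 | 47% |
| 3 | 2600 | 1200 | 32% |
| 4 | 3200 | 600 | 16% |
| 5 | 3800 | 0 | 0% |

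**Step 3. How long does the drug persist?** Section 6.1.5 gives a half-life of 172 ± 39 h, so T = 133, 172 or 211 h. Assume one compartment, with doses at 0, 7, 24, 48, 72 and 96 h (7 h is the midpoint of 6 to 8 h). Amount at time h = sum of dose × 2^(−(h − t)/T) over doses given at times t.

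- Full course at 96 h, T = 172: 3051 mg (2871 to 3172 across the range of T).
- Stopped after day 2, at 96 h: 1411 mg, and 1411/3051 = 46% (44% to 47%).
- Stopped after day 3, at 96 h: 1906 mg, and 1906/3051 = 62% (61% to 64%).
- After a full course, the share of the 96 h amount left is 2^(−48/172) = 82% on day 7 (78% to 85%), 2^(−120/172) = 62% on day 10 (54% to 67%) and 2^(−216/172) = 42% on day 14 (32% to 49%).

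Stopping early therefore lowers exposure materially on days 1 to 4. After day 5 drug is still present on this model, but stopping is no longer possible.

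**The case against.** **The missing text may exist elsewhere.** A participant-facing warning in an internet trial would normally sit in the consent form, a drug insert or the surveys. Consent pages were removed from the public file and the survey forms are not in it. This stands, and it limits the point to the protocol body.

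**Participants are not uninformed.** They screened themselves against the 5.2 list, are tested on knowing that they may be taking hydroxychloroquine, and can reach a physician. Entry exclusions for heart disease and QT history lower baseline risk. All of this reduces the concern, but none of it says what to do when a new prescription is written.

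**The protocol documents reassuring evidence.** Section 2.3.1 links QT prolongation to years of use and cites a review of short-term antimalarial trials with no serious cardiac events among 35,548 participants (1,076 on chloroquine). That belongs in the risk assessment. It does not settle the risk of combinations, which is what the reproduced caution addresses.

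**Leaving care to local providers is a deliberate pragmatic choice**, and half of the participants take placebo. Both are true. A cautionary instruction is compatible with both.

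**Four stronger readings are tempting but unsupported.**

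- A reader might infer that stopping is allowed only for side effects. Section 6.3 does not say only, and 5.3.2, 5.3.3 and 11.4 let anyone stop for any reason and remain in follow-up.
- A reader might infer from the visit lists in 7.3 that co-medication is certainly not asked about on days 3, 5 and 10. The day 1 list there also omits the query that 6.6 requires, so those lists are incomplete on this item and their silence proves little.
- A reader might take the 82%, 62% and 42% as a measure of harm. They are body amounts from a simple model, for a drug that 6.1.5 describes as widely distributed. An early distribution phase would put plasma levels lower, and the documents tie no level to QT risk.
- A reader might give antiarrhythmics equal weight. Nothing suggests that people screened for heart disease would commonly start one within 14 days. A listed antimicrobial is the plausible case.

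**Conclusion.** The point holds for the protocol body. Section 6.6 is permissive without exception, the 5.2 drug restrictions end at entry, and 2.3.1 relies on those restrictions as its cardiac mitigation although the stated reason for them, drug interaction, continues through exposure. What is missing is an instruction; permission to stop already exists.

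The window in which an instruction changes dosing is days 1 to 4, where it avoids between 63% and 16% of the course. From the end of day 5 it is advice only. The size of any harm is unknown, because the documents give neither a co-prescription rate nor an event rate. The persistence figures rest on one-compartment elimination at the stated half-life and are illustrative.

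The amendment is worth making for safety. It does not call the primary analysis into question.

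**What to change.** Amend 6.6 and the participant instructions in section 7 as follows.

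- Through day 14, a participant offered a drug listed in 5.2 tells the prescriber that they may be taking hydroxychloroquine and notifies the on-call study physician. Needed care is not delayed while they do so.
- If the drug is needed on days 1 to 5, the participant stops the remaining study tablets and stays in follow-up, analyzed by intention to treat.

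Survey items on listed drugs with start dates, and descriptive tables of co-exposure by arm, are optional extras.

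Costs:

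- Some calls to the study physician.
- A risk that notification is read as a precondition for treatment, which is why the wording must say that care is not delayed.
- A few more events in the all-cause discontinuation secondary endpoint; reporting the reason for stopping deals with this.
- Possibly slight dilution of the primary effect, because stops in the active arm also remove treatment. As an illustration, take the design rates of 10% and 5%. If stopping were unrelated to risk and lost all benefit, each 1% of the active arm that stopped would shrink the 5-point difference by 0.01 × 5 = 0.05 points. The true share is not known. The symptomatic cohort is the more exposed, since its members are already ill.
- Outside prescribing cannot be enforced.

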7 STUDY SCHEDULE

Screening Online Questionnaire

- Email [contact] or go to www.covidpep.umn.edu if you have been exposed to or diagnosed with COVID19
- You will be sent an email with information about our clinical trial
- A URL link will be provided for you to take the online screening survey

Medication Shipped

- Study medicine will be shipped overnight to your address
- Study medicine should arrive by 10:30am (Mon-Sat)
 - If you enroll after ~12pm on Sat or Sun, will arrive Tue.
- Take 4 tablets of the study medicine with some food or milk

Online Survey (Day 1)

- You will receive an email with a link to an online survey from [contact]. If not received, check your spam folder.
- Take the second dose of 3 tablets 6-8 hours after the first.
- Take other medicines \geq 4 hours apart from the study medicine

Study Days 2-4

- You should take 3 tablets each morning
- If you develop upset stomach, you may separate the pills; for example 1 at breakfast, 1 at lunch, and 1 at dinner.
- We will send a brief Day 3 survey

Online Survey (Day 5)

- You will receive an email with a link to an online survey
- This should be the same day you finish the study medicine
- A brief follow up survey will also be sent on Day 10 to ask if you have any COVID19 symptoms

End of Study Survey (Day 14)

- You will receive an email with a link to an online survey
- Unless you have developed symptoms, this marks the end of the study. We will ask if you wish to participate in future studies.
- If you were hospitalized or have pending tests, we will reach out to you every 2 weeks.

7.1 Screening

- Baseline screening for eligibility
- Informed consent by self-administered
- This will be performed via a web-based form. Eligibility criteria will be by self-report.

7.2 Enrollment/Baseline

Randomization (Day 0)

- Participants will be randomized by a computer-generated algorithm using a permuted block randomization sequence.
- Randomization will be stratified by symptomatic vs. asymptomatic status at baseline.
- Investigational pharmacy will dispense the masked study medicine
- Study personnel will then FedEx study medicine to the participant
- Participant will be sent an email to expect medication to arrive by 10:30am

7.3 Follow-up

Day 1 Virtual visit

- Verify receipt of study medicine
- Clinical status check-in
 - Participant starts study medicine (4 tabs), then 3 tabs in 6-8 hours, then 3 tabs daily.
- Query for SARS-CoV-2 testing
- Query for symptom status (0-10 visual analog scale of symptom severity)
- Query for hospitalization or SAEs
- Query for medication-related side effects / AEs

Day 3 Virtual visit

- Query for symptom status (0-10 visual analog scale of symptom severity)
- Query for hospitalization or SAEs
- Query for medication-related side effects / AEs

Day 5 Virtual visit

- Query for symptom status (0-10 visual analog scale of symptom severity)
- Assessment of adherence by self-report
- Completion of study medicine, which has a ~7 day half-life
- Query for study medicine side effects since enrollment
- Query for SARS-CoV-2 testing
- Query for hospitalization or SAEs

Day 10 Virtual visit

- Query for symptom status (0-10 visual analog scale of symptom severity)
- Query for SARS-CoV-2 testing

- Query for SARS-CoV-2 testing
- Query for hospitalization or SAEs

7.4 Final Study Visit

- Day 14 Visit
 - Query for symptom status (0-10 visual analog scale of severity)
 - Query for study medicine side effects since enrollment
 - Query for SARS-CoV-2 testing
 - Query for hospitalization or SAEs
 - Query for pregnancy status
 - Final outcome assessment
 - Assess other medicines used during study period
 - Optional dried blood spot collection, return in pre-paid envelope.

If participations have a SAE prior to the final study visit (e.g. hospitalization), the final resolution of the event will be followed until resolution or up to 90 days. The hospitalization eCRF will be sent in 14 days interval to assess clinical outcome / resolution of the hospitalization. Pregnancies will be followed through delivery to assess for any teratogenic SAE.

